9.5 INTERIM OPERATIONS (WHILE RECRUITMENT IS CONTINUING)

Safety

The following variables will be analyzed for the first 40 subjects after each subject has completed the study (or been withdrawn):

- Initial assignment (**Group 1A or 2A**)
- Subsequent assignments (Groups 2B and 2C)
- Site
- Ulcer area at randomization (TV1) through TV13
- Patients withdrawn
- Patients who experience infection (and visit number(s))

The report should show accrued data in aggregate and by site. The report should be available in Excel format.

If for some reason severe imbalances develop between groups or at sites, a new randomization scheme will be implemented with additional or modified stratification based on the most affected variables.

9.6 INTERIM ANALYSIS

One interim safety and efficacy analysis will be performed when approximately 110 subjects have been enrolled (approximately 50% of subjects). The total number of AEs and SAEs will be calculated, and the proportion of healed wounds tabulated for all groups (at 12 weeks). New sample size calculations will be performed based on the proportion of healed wound data (time to heal). No statistical analysis will be conducted.

TRIAL STOPPING RULES

The Medical Monitor may unblind, or appoint an independent assessor to unblind interim data analyses to determine whether the study should be stopped if any of the following occur:

- If the primary outcome likely has reached statistical significance and there is agreement to analyze the secondary outcomes regardless of whether they are likely to achieve statistical significance or not.
- If the primary outcome has likely not reached statistical significance and based on futility boundary analysis, the numbers of additional subjects needed to reach significance based on the rate data are too high to realistically extend the trial.
- $\geq 25\%$ of ulcers have deteriorated (meaning an increase in area from baseline to 12 weeks).
- A significant proportion of patients ($> 25\%$) in either group continue to experience infections despite Prisma/antimicrobial treatment or other measures
- Excessive non-planned withdrawal of subjects

List of variables for interim analysis

- Site ID
- Subject ID
- Treatment assignment
- Gender
- Pain score at baseline and 12 weeks
- Wound healed (Y/N) by 12 weeks (after 12 weeks have elapsed from date of randomization)
- When wound healed (days from randomization)
- Ulcer area at baseline and 6/12 weeks
- AEs (by category; have separate category for infected wounds) and SAEs at 12 weeks (count by subject, and description/category where applicable)
- Withdrawn subjects or subjects that have been lost to follow-up (count and by assignment with reason where applicable)
- Number of subjects in **Groups 2B and 2C**.

PATIENT POPULATIONS

The populations defined for the final analysis will include the intent-to-treat (ITT), per protocol (PP), and safety populations.

INTENT-TO-TREAT POPULATION

The ITT population will be analyzed for primary and secondary endpoints up to 12 weeks; however, Index Ulcers that have been healed are still subject to confirmed wound closure for 2 weeks later (up to 14 weeks for ulcers initially healed in the 12th week).

PRE PROTOCOL POPULATION

The PP population for the 12-week study will comprise all subjects for which no protocol violations occurred and in which for both groups' complete data are available for all primary and secondary endpoints, and all covariates needed to conduct adjusted analyses.

SAFETY POPULATION

The safety population will be all subjects who have received at least CelluTome™ treatment or have completed the first visit (randomization, TV1).

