5 STUDY POPULATION

5.1 NUMBER OF SUBJECTS

The study will consist of up to 30 centers in the United States each contributing about 10 subjects per center in order to obtain 300 evaluable subjects. We anticipate a 10% drop out rate during the trial for both Groups 1A and Group 2A, and 30% of subjects in Group 2A will switch to Group 2C and therefore a total of 225 subjects will be recruited. This trial employs an adaptive design therefore the enrollment numbers may be reduced or increased based on planned interim analysis.

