9.1.1 GENERAL

Descriptive statistical methods will be used to summarize the data from this study with hypothesis testing performed for primary and secondary endpoints. These include number of subjects (n), mean, median, standard deviation, minimum, and maximum for continuous data, and frequencies and percentages for categorical data. All data collected during the study will be reported and analyzed.

Unless specified otherwise, all statistical testing will be two-sided and performed using a significance (alpha) level of 0.05.

All statistical analyses will be conducted using PASW 19.

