9.3 SAMPLE SIZE CALCULATIONS

A two-sided logrank test with an overall sample size of 225 subjects (113 in the control group and 112 in the treatment group) achieves 86.1% power at a 0.05 significance level to detect a hazard ratio of 1.74 when the proportion of wounds healed in the control group is 0.5. The study lasts for 12 weeks with all subjects beginning the study together (no accrual periods). The proportion dropping out of the control group is 0.033 per week. The proportion dropping out of the treatment group is 0.0083 per week. The proportion switching from the control group to another group with a hazard ratio equal to that of the treatment group is 0.

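### The interim sample-size recalculation has no stated rule or limits and may depend on the observed group difference, so the final 0.05 log-rank test is not guaranteed to hold its level even if no efficacy stop is made

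*Combined protocol and SAP*

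**What the plan says.** Section 9.6 sets one interim look when about 110 subjects, roughly half, are enrolled. It has "the proportion of healed wounds tabulated for all groups (at 12 weeks"), and treatment assignment is on the list of interim variables. The next step is: "New sample size calculations will be performed based on the proportion of healed wound data (time to heal"). The section then says that no statistical analysis is done at this point. Its stopping rules include a discretionary futility option that considers how many more subjects would be needed for significance, judged from the rate data.

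Section 5.1 calls the design adaptive and says "the enrollment numbers may be reduced or increased based on planned interim analysis".

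Section 9.1.1 states that "all statistical testing will be two-sided and performed using a significance (alpha) level of 0.05" unless specified otherwise. Section 9.7 analyses the primary endpoint by Kaplan-Meier and an unadjusted log-rank test, followed by Cox regression. The only adjustment of the level is the Hochberg procedure across hypotheses, at the end of 9.7.

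The starting size in section 9.3 is an "overall sample size of 225 subjects (113 in the control group and 112 in the treatment group"). By the plan's calculation this size "achieves 86.1% power at a 0.05 significance level to detect a hazard ratio of 1.74", taking control-arm healing as 0.5.

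The plan does not give a recalculation formula, a minimum or maximum N, a conditional-power condition, a combination test or an adjusted final level.

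**The concern.** An ordinary final test at 0.05 assumes that the number of subjects was chosen without knowledge of the treatment difference. If the remaining enrollment is chosen from the observed difference, the final statistic no longer has its standard null distribution. Extending after a weak look gives the test a fresh chance. Cutting after a favourable look locks in a lucky start. Both raise the false-positive rate.

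This needs no interim p-value, so the statement that no statistical analysis is done does not remove it. It is also distinct from early stopping for efficacy: a stopping boundary would leave it in place. What is at stake is the error rate of the primary superiority claim.

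**Working it through.** **1. Reproduce the plan's own figure.** Inputs from 9.3: 113 control and 112 treatment subjects, 12 weeks, control healing 0.5, hazard ratio 1.74, weekly dropout 0.033 (control) and 0.0083 (treatment).

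- Control hazard = ln 2 / 12 = 0.0578 per week. Treatment healing without dropout = 1 − 0.5^1.74 = 0.70.
- A Markov (Lakatos-type) calculation gives about 48 + 75 = 123 events and power of 85.7% (fine steps) to 86.6% (weekly steps).
- Schoenfeld check: Φ(√123/2 × ln 1.74 − 1.96) = Φ(3.07 − 1.96) = 86.7%.

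The stated 86.1% is reproduced, so the starting size is not in question here.

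**2. A plain observed-difference rule (assumed, since none is stated).** Let z1 be the interim statistic on 110 subjects, and keep 86.1% power at the observed effect:

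N = 110 × ((1.96 + 1.085) / |z1|)² = 1020 / z1², clipped to chosen limits.

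This gives N = 110 at |z1| = 3.04, 225 at 2.13, 300 at 1.84 and 450 at 1.51.

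**3. The final ordinary test under the null.** Z = √(110/N) z1 + √(1 − 110/N) z2, rejecting if |Z| > 1.96. The chance of rejection given z1 shows the mechanism:

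- z1 = 0.5 (weak look): 1.3% at N = 225, 3.0% if N is raised to 450.
- z1 = 2.5 (favourable look): 38% at N = 225, 56% if N is cut to the 163 that the rule asks for.

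**4. Overall two-sided type I error.** This integrates step 3 over the null distribution of z1, with no efficacy stop:

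| Limits on N (assumed) | Type I error |
|---|---|
| Fixed at 225 | 5.00% |
| 225 to 300 | 5.37% |
| 225 to 450 | 5.85% |
| 110 to 300 | 5.91% |
| 110 to 450 | 6.39% |
| 110 to 900 | 6.99% |
| 110, no cap | 7.54% |

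A patient-level log-rank simulation (20,000 runs per setting, Monte Carlo standard error about 0.17 points) gave 6.3% (110 to 300), 6.9% (110 to 450) and 6.2% (225 to 450), against 4.9% to 5.2% with N fixed. If only 60 to 80 subjects have 12-week data at the look, the rule gives 5.3% to 7.1% for caps of 300 to 900.

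**5. Other rules that the text also permits.**

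- Pooled healing rate with the hazard ratio held at 1.74 (110 to 450): 4.8% in simulation, the same as with N fixed in those runs.
- Control-arm rate with the hazard ratio held fixed: 4.9% to 5.2%.
- N raised only when conditional power is at least 50%: about 4.8%.
- Observed difference, keeping 225 whenever the required N exceeds 450: 4.8% to 5.3%.
- Observed difference, with a binding futility stop when the required N exceeds the cap (minimum 110): 2.4% (cap 300) to 4.1% (cap 900).

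**6. Check of the remedy.** With fixed weights, Z = √(110/225) Z1 + √(115/225) Z2 has type I error 5.00% whatever second-stage size is chosen.

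**The case against.** The strongest objection is that the plan never says the new size uses the observed difference. The only healing proportion in the 9.3 calculation is the control value, and the effect is entered separately as a hazard ratio. Updating that control value with the hazard ratio held at 1.74 is a fair reading of 9.6, and step 5 shows that it does no harm. This stands. A reader might infer that the final test fails its level, or that using by-group data inflates the error in itself. The documents support neither, because the rule is missing and several permitted rules hold about 5%.

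It does not clear the plan, however. The interim input is healing by group. The futility bullet counts the subjects needed for significance from the rate data, which points towards the observed difference. Nothing restricts the recalculation to a nuisance rate.

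Other points on that side:

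- **Futility.** A binding stop would bring the error below 5%, but the stop in 9.6 is discretionary and cannot be relied on.
- **Hochberg.** It addresses several hypotheses, not a data-dependent N.
- **Overlap with an efficacy stop.** With a minimum of 110, the trial ends at the look and rejects when |z1| reaches 3.04. That has probability of only about 0.2% under the null, and the cases with a minimum of 225 are free of it.
- **Size.** The caps of 450 and 900 are assumptions. The only larger figure in the documents is the 300 in 5.1, which is not stated as a cap. With 300 as the limit, the error is 5.4% to 5.9%.

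**Conclusion.** The concern holds in this form: the recalculation rule and its limits are unstated, and the observed group difference is not excluded, so the final log-rank test is not guaranteed to hold 0.05.

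Under a plain observed-difference rule the error is about 5.4% to 5.9% if N can only rise from 225 (cap 300 to 450). It is 5.9% to 7.0% if N can lie between 110 and a cap of 300 to 900, and about 7.5% with no cap. To bring that rule back to 0.05 with a minimum of 110, the final nominal level would have to be about 0.041 (cap 300) or 0.037 (cap 450).

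The least favourable choice of N at each interim result gives 9.3% (110 to 300) to about 11% (no cap). A reader might take that as the expected inflation. It is only an upper bound, since nothing in the documents suggests that N would be chosen that way.

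These figures assume the rule in step 2, the limits shown, complete 12-week data on 110 subjects unless noted, and a single primary comparison. The paired 6- and 12-week comparisons and the later split of the control group are separate matters and are not counted.

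**What to change.** This is a cheap improvement: SAP wording in 9.6, settled before any interim data are seen.

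- **Preferred.** State that the size is recalculated only from the pooled healing proportion and loss rate (both arms combined), with the hazard ratio held at 1.74. State the minimum and maximum N in advance. No floor of 225 is needed for error control, so the reduction allowed in 5.1 can stay.
- **If the observed effect is to be used.** Replace the final test by a log-rank combination of the two stages, with the first 110 subjects as stage one and later subjects as stage two. Fix the weights in advance at 110/225 and 115/225 (square roots of these applied to the stage statistics).
- **By-group efficacy data.** If these are needed for the stopping bullets in 9.6, they should not feed the recalculation. Say who sees them.

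The cost is that under the pooled rule the size can no longer respond to the observed effect. Under the combination test, subjects in the two stages count unequally if N changes. Neither option alters visits or procedures.

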The Treatment Phase (TV1 to TV13) Begins with a series of assessments designed to confirm the subjects’ continued eligibility. Investigators will debride the ulcer. Subjects whose ulcers continue to meet eligibility criteria will then be randomized to one of two groups: (1) One application of epidermal microdome at day zero and standard of care (**Group 1A**) OR (2) standard of care: multi-layer compression (**Group 2A**) (see figure on next page).

During the Treatment Phase, subjects will be evaluated on a weekly basis. Effectiveness evaluations each week will include Investigator assessment of wound healing and measurements of ulcer size using digital photos.

At TV 7, wound assessment will be carried out to evaluate wound healing in **Group 2A**. Subjects in **Group 2A**, whose percentage area reduction (PAR) is <40% will be allowed to have CelluTome™ treatment in addition to continuation of SOC and will constitute **Group 2C**. **Group 2C** will receive a graft at TV7 and TV11. The remainder of **Group 2A** subjects will be termed **Group 2B** subjects. Patient codes will still remain the same to enable tracking continuity.

[figure not shown]
During the Treatment Phase, the wound will be swabbed for protease activity for **Group 1A and 2A/B** subjects: TV1 (In **Group 1A** this will be prior to CelluTome™ application), TV5 and TV9 visits.

Subjects will be evaluated on a weekly basis during the Treatment Phase. Effectiveness evaluations each week will include Investigator assessment of wound healing and measurements of ulcer size using digital planimetry. At TV4 and TV8, Prisma™ is to be applied to the study ulcer for **Groups 1A, 2A, and 2B** subjects. **Group 2C** subjects will receive Prisma™ at TV10. Safety evaluations during the Treatment

CELLUTOME™ IN VENOUS LEG

Phase will consist of adverse event assessments at each visit.

Diagram showing progress of trial and the different subjects groups. Up to 6 weeks from randomization only **Groups 1A and 2A** exist; after 6 weeks, **Groups 1A, 2B, and 2C** exist.

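### Section 9.6 allows an efficacy stop with no boundary or alpha spending, yet says no statistical analysis is done, so the two-sided 0.05 error rate is not guaranteed

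*Combined protocol and SAP*

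**What the plan says.** Section 9.6 schedules one interim safety and efficacy analysis at about 110 enrolled subjects. It asks for "the proportion of healed wounds tabulated for all groups (at 12 weeks"), and continues: "New sample size calculations will be performed based on the proportion of healed wound data (time to heal). No statistical analysis will be conducted".

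The stopping rules follow at once. "The Medical Monitor may unblind, or appoint an independent assessor to unblind interim data analyses" in order to decide whether to stop. The first ground is "If the primary outcome likely has reached statistical significance and there is agreement to analyze the secondary outcomes regardless" of how those outcomes are likely to turn out. The second is futility, where, "based on futility boundary analysis, the numbers of additional subjects needed to reach significance" are judged unrealistic. Neither ground comes with a criterion. The interim variable list includes treatment assignment, days to healing and "Wound healed (Y/N) by 12 weeks (after 12 weeks have elapsed from date of randomization").

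Elsewhere in the same document:

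- Section 5.1 calls the design adaptive and lets enrolment rise or fall after the interim.
- Section 9.1.1 sets two-sided 0.05 for all tests, and Section 9.3 computes power at 0.05.
- The only multiplicity adjustment, at the end of Section 9.7, is a Hochberg procedure across hypotheses.
- Section 9.2 (H1) has two primary comparisons: Group 1A versus 2A at 6 weeks and 1A versus 2B at 12 weeks. Group 2B is what remains after the Group 2A subjects "whose percentage area reduction (PAR) is <40% will be allowed to have" the graft have moved to Group 2C (Section 4).

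**The concern.** Neither stopping ground can be applied without some statistical assessment of the arms, so Section 9.6 contradicts itself. The contradiction matters because a by-arm look that can end the trial as positive spends alpha, whether or not a formal p-value is printed. Hochberg orders p-values from different hypotheses at one time point and does nothing about testing the same hypothesis twice.

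If the rule were used, neither an early positive stop nor a final p just under 0.05 could be defended at the stated level, and this cannot be repaired after unblinding. Section 9.6 also does not say which of the two primary comparisons governs the stop (its healing variables lean to 12 weeks), or how by-arm data may enter the re-sizing.

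**Working it through.** **Inputs from the plan.** 113 control and 112 treated subjects, hazard ratio 1.74, 50% of controls healed (taken at 12 weeks), weekly dropout 0.033 and 0.0083, 86.1% power at 0.05 (Section 9.3); look at about 110 subjects (Section 9.6); 300 as a possible larger size (Section 5.1).

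**Assumed, because the plan gives neither.** Interim cut from 0.005 to 0.10. Information fraction t from 0.2 to 0.7, with 110/225 = 0.49 as the working value. The look is triggered by enrolment, so t in healing events is not fixed.

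**1. The plan's power.** Hazards are ln2/12 = 0.0578 per week (control) and 1.74 times that, 0.1005 (treated). Expected events are n·λ/(λ+δ)·[1 − exp(−12(λ+δ))], where λ is the healing hazard and δ the weekly dropout: 47.7 + 75.4 = 123.1. Schoenfeld: √(123.1/4) × ln 1.74 − 1.96 = 3.07 − 1.96 = 1.11, or 86.7%. Freedman's formula gives 85.0% and a Lakatos-type model 85.7%. The 86.1% reproduces at the full 0.05, with nothing set aside for a look.

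**2. Type I error.** With no effect, the interim and final statistics are bivariate normal with correlation √t. The error is P(|Z1| > c1 or |Z2| > 1.96) if every crossing stops the trial.

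| Interim cut (two-sided p), t = 0.49 | Type I error |
|---|---|
| 0.005 | 5.2% |
| 0.01 | 5.5% |
| 0.02 | 6.1% |
| 0.05 | 8.3% |
| 0.10 | 12.5% |

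For the 0.05 cut the error is 9.2% at t = 0.2, 8.9% at 0.3, 8.7% at 0.37 and 7.6% at 0.7. If only a share q of crossings at 0.05 leads to a stop, at random, the error at t = 0.49 is 0.05 + q(0.0835 − 0.05): 5.8%, 6.7% and 7.5% for q = 0.25, 0.5 and 0.75.

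**3. Spending levels at t = 0.49** (√t = 0.699), all as nominal two-sided p-values.

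- O'Brien-Fleming-type spending of two-sided 0.05: the interim level is 2[1 − Φ(1.960/0.699)] = 0.0051. Solving for a total of 0.05 gives a final level of 0.0480.
- Spending 0.025 on each side: the interim level is 4[1 − Φ(2.241/0.699)] = 0.0027, and the final level is 0.0491.

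**4. Re-sizing.** If the interim used 0.0051 against 225 and the total then changes, the final level must be solved again with the new t. For 300 (t = 110/300 = 0.37) it is 0.0472. For 157 (t = 110/157 = 0.70) it is 0.0493. Levels computed as if the new total had been known at the look (final 0.0495 and 0.0430) do not apply. Pairing 0.0051 with 0.0495 at t = 0.37 gives a total of about 5.2%.

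**5. Power cost.** 86.1% corresponds to a drift of 1.960 + 1.085 = 3.045. Power is 1 − P(Z1 < c1, Z2 < c2) with means 3.045√t and 3.045. At t = 0.49 it is 85.8% for two-sided spending and 86.0% for spending per side. At t = 0.70 two-sided spending gives 85.3%.

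**6. The 12-week comparison, 1A versus 2B.** This was simulated with no treatment effect, weekly visits, equal exponential healing and 50% healed at 12 weeks. Following Section 5.1 ("30% of subjects in Group 2A will switch to Group 2C"), 30% of controls leave from among those unhealed at week 6. Mean log-rank Z (negative favours SOC):

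| Handling of switchers | 55/55 | 112/113 |
|---|---|---|
| Random, censored at week 6 | 0.01 | 0.00 |
| Slowest healers, censored at week 6 | −1.03 | −1.51 |
| Random, removed | −0.97 | −1.44 |
| Slowest healers, removed | −1.99 | −2.96 |

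**The case against.** The best defence is the sentence itself: if no analysis is conducted, nothing is tested and no alpha is spent. On that reading the added error is zero, and strict cuts of 0.005 or 0.01 would add only 0.2 to 0.5 points. This stands as one end of the range. It does not remove the point, because the efficacy ground stays in the plan and the by-arm data needed to use it are on the interim list.

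Three stronger readings are tempting, and the documents do not support them.

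- A reader might infer that the trial's error rate is 8.3%. That needs a cut of 0.05, t = 0.49 and a stop at every crossing. The plan states none of these, and stopping is discretionary.
- A reader might take 8.3% as a ceiling. Discretion lowers the figure for a given cut and t, but a smaller t or a looser reading of the word likely raises it.
- A reader might infer that the 12-week comparison is always off-centre, or that it adds to the false-positive risk for the device. Neither follows. Any bias there favours SOC. It is about zero if switchers are effectively random among unhealed controls and are censored at week 6. Censoring is a live reading: Section 9.7 right-censors missing primary data, and the control dropout in Section 9.3 (12 × 0.033 = 0.40) matches 10% dropout plus 30% switching in Section 5.1. Selection on area reduction is unlikely to be random, so some bias is plausible, but its size depends on a handling rule that the plan does not give.

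**Conclusion.** The point holds as a contradiction with a missing boundary: Section 9.6 denies any analysis and yet permits an efficacy stop, and nothing in the plan protects the two-sided 0.05 against that look. The excess error runs from none (no efficacy decision ever taken) to 3.3 points (cut 0.05, t = 0.49) or 7.5 points (cut 0.10, t = 0.49). The cut, t and automatic stopping are assumptions throughout. The figures are for one randomised comparison. They exclude any further inflation from data-driven re-sizing, and no family-wise figure is given because Section 9.7 does not define the Hochberg family.

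The 1A versus 2B comparison is a separate problem. Group 2B is selected after randomisation, and with no effect its mean Z at the final analysis lies anywhere from about 0 to about −3. That is a reason not to let it govern a stop, and it is not part of the error figures above.

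This should be settled before any interim data are unblinded.

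**What to change.** Reconcile the statement that no analysis is done with the stopping rules, then choose one of two routes.

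1. **Delete the efficacy ground.** If a futility rule is kept, state its criterion and call it non-binding.
2. **Pre-specify an O'Brien-Fleming-type spending function.** Say whether it spends two-sided 0.05 or 0.025 per side; at t = 0.49 the nominal two-sided levels are about 0.0051/0.0480 or 0.0027/0.0491 respectively. Name the comparison that governs the stop; of the two primaries only 1A versus 2A at 6 weeks is randomised. State the maximum information that defines t at the look, and compute the final level from the alpha actually spent and the observed information, as in step 4 of the working.

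In either case, state the re-sizing rule. Pooled, arm-blind healing data are simplest. If by-arm data are used, name a method that controls type I error.

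**Cost.** A wording amendment with IRB approval (Sections 13.2 and 14.1), made before any unblinding. Deleting the efficacy ground costs no power. A futility rule that is acted on does: at t = 0.49, stopping for conditional power below 10% costs under 0.1 point if computed under the design effect and about 3 points (86.1% to about 83%) under the current trend. Spending costs about 0.1 to 0.3 points near t = 0.49 and up to about 0.8 at t = 0.70. These losses are from the 12-week power, the only one the plan states. It gives none for 6 weeks; if that were about 70% (an assumption), two-sided spending would cost 0.4 to 1.1 points.
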